#### 5.4.3 Dose modification or delay durations and modification levels (after phase Ib)

Day 8 dose of eribulin may be delayed for a maximum of 1 week. If toxicities do not improve enough after 1 week delay then omit day 8 dose of eribulin. If day 8 of eribulin is omitted two consecutive cycles eribulin should be resumed at one dose below current dose level.

##### Eribulin dose modification levels

Dose level 0	1.1mg/m 
Dose level -1	0.7 mg/m 

##### Lenvatinib dose modification levels

Dose level 0	18 mg /day
Dose level -1	14 mg/ day

Dose level -2	10 mg/ day
Dose level -3	8 mg/ day

## 5.5 Duration of the treatment

- Patients may continue on study therapy until disease progression or until unacceptable toxicity occurs.
- Patients will go off study therapy if any of the following occurs:
  - The patient experiences any grade 4 toxicity after 2 dose modifications, as recommended by the protocol. If treatment is held for 2 consecutive treatment cycles due to toxicity, the patient must go off treatment.
  - The patient withdraws consent from treatment or from the study as a whole.
  - There is disease progression.
  - The treating physician feels it is necessary (e.g. due to patient non-compliance or other safety concerns)

## 6 Study Assessment/ Procedural Schedule

### 6.1 Pre-treatment baseline evaluation

Table 6 Assessments necessary before randomization

Investigations		Timing prior to treatment
Informed consent		within 28 days
Criteria	All inclusion criteria met All exclusion criteria not met	within 28 days
Medical History	Initial sarcoma AJCC stage Previous chemotherapy and hormonal therapy treatment history Radiotherapy history	within 28 days
Physical Exam	Height, Weight, Blood pressure Karnofsky Performance status Existing symptoms and signs Concurrent medications	within 14 days
Hematology	CBC Differential	within 14 days

	Coagulation	
Biochemistry	Serum creatinine and creatinine clearance a BUN Electrolytes (Na, Ca, K, Mg) Albumin Total bilirubin Alkaline phosphatase AST and ALT LDH Urinalysis Serum or urine pregnancy test b	within 14 days
Imaging	Chest / Abdominal/pelvis CT scan (or MRI if patient is contraindicated for CT)	within 28 days
Other Investigations	12-Lead ECG	within 14 days
a May be calculated using Cockcroft-Gault formula. b Required for women of childbearing potential only within 72 hours of registration.		

## 6.2 Pre- treatment assessments

Table 7 Assessments necessary before every cycle of treatment

Investigations		Timing prior to administration of treatment
Medical History	Previous treatment toxicity	within 3 days
Physical Exam	Height, Weight, Vital signs Karnofsky performance status Existing symptoms and signs Concurrent medications	within 3 days
Hematology	CBC Differential	within 3 days

Biochemistry	Serum creatinine and creatinine clearance a BUN Electrolytes (Na, Ca, K, Mg) Total protein/ Albumin Total bilirubin Alkaline phosphatase AST and ALT LDH Urinalysis	within 3 days
a May be calculated using Cockcroft-Gault formula.		

### 6.3 Tumor Assessment during treatment

#### 6.3.1 Tumor imaging criteria—RECIST 1.1

1. The tumor response will be determined by applying **RECIST 1.1**. Assessment schedule of week 8, 16, 24 and every 12 weeks afterwards, according to the regulation of the payment of image study by National Health Insurance. The measurability of a tumor is defined as follows:

- **Measurable disease** - the presence of at least one measurable lesion. If the measurable disease is restricted to a solitary lesion, it can be still be considered as a measurable target according to its clinical course.
- **Measurable lesions** - lesions that can be accurately measured in at least one dimension with longest diameter  $\geq 20$  mm using conventional techniques or  $\geq 10$  mm with spiral CT scan.
- **Non-measurable lesions** - all other lesions, including small lesions (longest diameter  $< 20$  mm with conventional techniques or  $< 10$  mm with spiral CT scan) and inflammatory breast disease.

All measurements should be taken and recorded in metric notation, using a ruler or calipers. All baseline evaluations should be performed as closely as possible to the beginning of treatment and never more than 4 weeks before the beginning of the treatment.

The same method of assessment and the same technique should be used to characterize each identified and reported lesion at baseline and during follow-up. Clinical lesions including skin nodules and palpable lymph nodes will be considered measurable when they are superficial. For the case of skin lesions, documentation by color photography, including a ruler to estimate the size of the lesion, is recommended.

#### 2. Methods of measurement

CT and MRI are the best and reproducible methods currently available to measure

target lesions selected for response assessment. Spiral CT should be performed using a 5 mm contiguous reconstruction algorithm.

### 3. Baseline documentation of "Target" and "Non-Target" lesions

All measurable lesions up to a maximum of five lesions in total (maximum two lesions in one organ) should be identified as target lesions and recorded and measured at baseline.

- Target lesions should be selected on the basis of their size (lesions with the longest diameter) and their suitability for accurate repeated measurements (either by imaging techniques or clinically).
- A sum of the longest diameter (LD) for all target lesions will be calculated and reported as the baseline sum LD. The baseline sum LD will be used as reference by which to characterize the objective tumor.
- All other lesions (or sites of disease) should be identified as non-target lesions and should also be recorded at baseline. Measurements of these lesions are not required, but the presence or absence of each should be noted throughout follow-up.

### 4. Evaluations included following the RECIST 1.1

- Complete response (CR): the disappearance of all known disease, determined by two observations not less than 4 weeks apart.
- Partial response (PR): A 30% or greater decrease in the sum of LD of all lesions in reference to the baseline sum LD. In addition, there may be no appearance of new lesions or progression of any lesion.
- Stable disease (SD): Neither sufficient increase to qualify for PD nor sufficient shrinkage to qualify for PR.
- Progressive disease (PD): A 20% or greater increase in the sum of LD of all target lesions, taking as reference the smallest sum LD recorded at or following baseline.
- Once a patient reached PR or CR of his/her tumor assessment, another image will be done 4weeks later. A confirmed PR or CR is defined as both these image tumor assessment is in the same category (PR or CR).

#### 6.3.2 Assessment schedules

- Tumor assessment by CT scan or MRI will be obtained at baseline (as specified in section 6.1), 8 weeks, and 16 weeks and 24 weeks and every 12 weeks afterwards. A +/- 7 days window is acceptable.
- Investigator assessment of the tumor response will be recorded and the investigator will decide treatment plan according to local assessment.

#### 6.3.3 Toxicity assessment

- Each patient will be evaluated for toxicity at baseline, every visit, and as needed at any time during the treatment, based on CTCAE 4.03 criteria.

#### **6.3.4 Follow up of patient status**

- Patients with grade 3 or 4 toxicity after treatment will be followed-up until the toxicity resolved to grade 1 or 2.
- All patients will be followed for survival at least 6 months after end-of-treatment. Follow-up interval should be every 8 weeks +/- 1 week.

#### **6.4 Biopsy during the study**

- A biopsy of either the primary or metastatic tumor will be taken at baseline (within 4 weeks of initiation of treatment) and after the first tumor assessment. If a disease progression is noted before cycle 3, a biopsy is still suggested.
- Biopsy samples will be used for biomarker testing that included: FGFR pathway analysis and NanoString platform for mRNA analysis of tumor immune microenvironment and biomarker assessment.
- A pre-treatment biopsy will be mandatory for at least 10 patients. If there is a safety concern regarding biopsy, the biopsy could be waived after discussion with the Principal Investigator. The second biopsy will be optional but is strongly suggested.
- A 10ml blood will be drawn +/- 3 days of each biopsy for peripheral blood (PB) analysis and the comparison between PB changes and association with the tumor microenvironment

#### **6.5 Summary Table**

Table 8 Flow sheet of LEADER Trial

Study	Screening		L + E Cycle 1 (21 days/cycle)			L + E Cycle 2 (21 days/cycle)			L+E Cycle 3 and afterwards (21 days/cycle)			End of Treatment i
			1 a	2	3	4	5	6	7	8	9	
Week	0		1 a	2	3	4	5	6	7	8	9	
Time window	-28~0	-14~0	-3~0	-3~0		-3 ~ +3 k	-3 ~ +3 k		-3 ~ +3 k	3 ~ +3 k		
Informed consent	X											
Inclusion/ Exclusion criteria	X											
Medical history b	X											
Physical examination		X	X	X		X	X		X j			X
Performance status (KPS or ECOG)		X	X			X						X
Laboratory assessments												
Hematology (CBC+diff, plts)		X	X	X		X	X		X			X
Serum chemistry c		X	X	X		X	X		X			X
Coagulation		X										
Urinalysis		X				X			X			X
Pregnancy test d		X	X									
Adverse event assessment e		X	X	X	X	X	X	X	X	X	X	X
Tumor assessment f		X								X		
12-Lead ECG g		X				X			X			X
Biopsy h	X (within 4 weeks)									X h		

L: Lenvatinib, E: eribulin, CBC: complete blood chemistry, ECG: electrocardiogram, KPS: Karnofsky performance status, ECOG: Eastern Cooperative Oncology Group

- a Medical history, physical examination, vital signs, Karnofsky or ECOG performance status, ECG, adverse events assessment, and concomitant medications may be omitted on Day 1 if these evaluations have been completed within 14 days prior to starting study treatment. Hemogram and biochemistry needs to be repeated within 3 days of Day 1.
- b History only – survival status, details of recurrent/metastatic disease, new treatments.
- c Serum creatinine and creatinine clearance, BUN, Electrolytes (Na, Ca, K, Mg), Total protein, Albumin, Alkaline phosphatase, AST and ALT, Total bilirubin, and LDH.
- d Women of childbearing potential
- e AEs recorded at every visit, and as needed at any time during the treatment. After end of treatment, AEs will be recorded until 28 days after end of treatment (EOT). The investigator is not required to actively monitor patients for adverse events afterwards. However, the sponsor should be notified if the investigator becomes aware of any post-study serious adverse events or non-serious adverse events of special interest. Other AE reporting details please refer to section 9.3.
- f Tumor assessment by CT or MRI will be carried out on week 8, week 16, week 24, and every 12 weeks afterwards with a +/- 7 days window. The week 8 and week 24 images will be sponsored by the study and week 16 and images after week 24 will be performed according the National Health Insurance Payment system. If a patient reached CR or PR according to RECIST on the 8-, 16-, or 24-week cycle, a confirmed imaging more than 4 weeks later will be sponsored by the study.
- g 12-Lead ECG will be performed before every cycle to monitor the QTc for the first 4 cycles, then every 9 weeks afterwards.
- h The first biopsy will be performed within 4 weeks of treatment starts, the second biopsy will be taken after 1st tumor assessment. At least 10 patients are required to take the pre-treatment biopsy and the second biopsy after treatment is optional but strongly suggested.
- i Survival follow-up interval is 8 weeks +/- 1 weeks for at least 6 months or death
- j If in later cycles patient is using only lenvatinib as single agent treatment, D8 visit and blood test could be omitted
- k two eribulin injections should be at least  $\geq 5$  days apart

## 7 Endpoints for Evaluation

### 7.1 Primary endpoint: Objective response rate (ORR) by RECIST 1.1

- Complete response (CR): the disappearance of all known disease, determined by two observations not less than 4 weeks apart.
- Partial response (PR): A 30% or greater decrease in the sum of LD of all lesions in reference to the baseline sum LD. In addition, there may be no appearance of new lesions or progression of any lesion.
- Stable disease (SD): Neither sufficient increase to qualify for PD nor sufficient shrinkage to qualify for PR.
- Progressive disease (PD): A 20% or greater increase in the sum of LD of all target lesions, taking as reference the smallest sum LD recorded at or following baseline.
- Once a patient reached PR or CR of his/her tumor assessment, another image will be done 4weeks later. A confirmed PR or CR is defined as both these image tumor assessment is in the same category (PR or CR).
- An ORR is defined as the either a CR or PR as defined by RECIST 1.1
- The best response as defined by RECIST 1.1 will be used for ORR assessment. The best response is defined as the most proximal response assessment before disease progression. If the first response evaluation showed disease progression, then the best response is PD.

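### The written partial-response rule compares all lesions with a target-only baseline sum, and the PR, SD and PD bullets leave some patients without a category

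*Combined protocol and SAP*

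**What the plan says.** The response definitions appear twice in the combined protocol and SAP, in almost identical words: in Section 6.3.1, item 4, and in Section 7.1.

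- **PR, size part (7.1):** "A 30% or greater decrease in the sum of LD of all lesions in reference to the baseline sum LD".
- **PR, exclusions (7.1):** "In addition, there may be no appearance of new lesions or progression of any lesion". The documents do not define progression of a single lesion.
- **PD (7.1):** "A 20% or greater increase in the sum of LD of all target lesions, taking as reference the smallest sum LD recorded" at or after baseline. The bullet has no clause on new lesions, non-target lesions or single lesions.
- **SD (7.1):** "Neither sufficient increase to qualify for PD nor sufficient shrinkage to qualify for PR".
- **Baseline sum (6.3.1, item 3):** "A sum of the longest diameter (LD) for all target lesions will be calculated and reported as the baseline sum LD". Target lesions are limited to five in total and two per organ.
- **Non-target lesions (6.3.1, item 3):** "Measurements of these lesions are not required, but the presence or absence of each should be noted throughout follow-up".

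Sections 6.3.1 and 7.1 also say that response, ORR and best response follow RECIST 1.1. Neither says whether the written bullets or RECIST 1.1 prevails where they differ. Section 6.3.2 has tumour response read by the investigator, and Section 10.6 names two enrolling institutions. No central reading is described.

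**The concern.** These bullets decide who counts as a responder for the primary endpoint. Two things do not fit together.

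First, for any patient with non-target disease, the follow-up sum in the PR rule covers more lesions than the baseline it is compared with. It also needs measurements that the protocol does not ask for. The PD bullet in the same list uses the target sum, so the two rules disagree on which lesions count.

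Second, PR can be refused for reasons that the PD bullet does not recognise, while SD is defined by size alone. A patient refused PR for such a reason may fit none of the categories.

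Both faults work in one direction, against PR. With few responses expected, one patient scored differently can change the result. Two sites reading locally could each settle on a different interpretation.

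**Working it through.** **1. The plan's own design figures.** Section 8.1 gives P0 = 0.05, P1 = 0.20, type I error 0.05, power 80%, stage 1 of 13 patients (stop if 0 responses), 27 evaluable and 30 enrolled. The final cut-off is not stated. With n1 = 13, n = 27 and success at 4 or more responses,

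P(success) = sum over x = 1 to 13 of C(13,x) p^x (1-p)^(13-x) × P(Y ≥ max(0, 4-x)), with Y ~ Bin(14, p).

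This gives 0.0416 at p = 0.05 and 0.8011 at p = 0.20. A search for the smallest total size that meets both limits returns the same design, 0/13 and 3/27. A cut-off of 3 or more has type I error 0.135, and 5 or more has power 0.645, so 4 or more is the only one that fits. Enrolment: 27/0.9 = 30. The stated 13/27/30 is reproduced.

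**2. PR sum read literally.** Let T be the target sum and N the non-target sum. The written rule compares (T + N) at follow-up with T at baseline. Since N ≥ 0, this ratio is never below the target-only ratio, so the wording can remove a PR but never create one.

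Invented patient: targets 50 + 50 mm become 30 + 30 mm; one non-target lesion stays at 20 mm.

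- Literal rule: (60 + 20)/100 - 1 = -20%, not PR.
- Target sum: 60/100 - 1 = -40%, PR on size.

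If all lesions shrink by the same fraction s and the baseline non-target sum is k times the target sum, literal PR needs (1 + k)(1 - s) ≤ 0.70, so s ≥ 1 - 0.70/(1 + k). The values of k are assumed:

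| k | shrinkage needed |
|---|---|
| 0 | 30.0% |
| 0.2 | 41.7% |
| 0.5 | 53.3% |
| 1.0 | 65.0% |

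**3. Do the categories cover everyone?** Take a patient whose target sum is at least 30% below baseline, has not risen 20% from its lowest value, and who has a new lesion.

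- PR: no, new lesions bar it.
- PD: no, the bullet looks only at the target sum.
- SD: no, the shrinkage is large enough for PR.

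No category applies, and this needs no interpretation of an undefined term. By contrast, the Choi definition in Section 7.2.5 does list new lesions as progression.

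A single growing lesion is less clear. Targets 60 + 12 mm becoming 30 + 15 mm give 72 to 45 mm, (45 - 72)/72 = -37.5%, with one lesion up 15/12 - 1 = +25%. PR is lost only if that growth is called progression, which the documents do not settle.

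**4. What a loss of responders would do.** The documents give no loss rate. If a fraction f of true responders were missed at a true ORR of 20%, the recorded rate is p = 0.20(1 - f), and the chance of stopping at stage 1 is (1 - p)^13:

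| f (assumed) | p | power | chance of 0/13 |
|---|---|---|---|
| 0 | 0.20 | 0.801 | 0.055 |
| 5% | 0.19 | 0.765 | 0.065 |
| 10% | 0.18 | 0.724 | 0.076 |
| 20% | 0.16 | 0.629 | 0.104 |

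**The case against.** The best defence is that RECIST 1.1 is the named standard. Section 6.3.1 says response is determined by it, Section 7.1 defines ORR and best response by it, and a footnote to the flow sheet in Section 6.5 ties confirmatory imaging to it. On this view the bullets are loose paraphrase. Moreover, the only sum the protocol requires is the target sum, so assessors would probably use it.

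This is a good reason not to claim too much. A reader might infer that clear responders will be denied PR, that any growth in any lesion cancels a response, or that the ORR tested will not be a RECIST 1.1 rate. The documents support none of these. The exclusion speaks of progression, not growth, and the only numerical progression threshold applies to the target sum. An extreme case such as six 20 mm lung lesions, two of them targets, would read 120 mm against 40 mm, or +200%, on the baseline scan itself; no site is likely to score that way. The loss rates in the table are assumptions.

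It can also be said that an assessor who refuses PR would naturally fall back on SD. That may happen, but the SD bullet does not say so.

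The defence does not remove the inconsistency. Item 4 of Section 6.3.1 presents these bullets as the RECIST 1.1 evaluations, and nothing tells an assessor to set them aside where they conflict with the baseline definition.

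**Conclusion.** The point holds as an internal inconsistency in the responder definition of the primary endpoint. The PR bullet does not match the protocol's own baseline sum, and the written PR, SD and PD bullets leave at least one ordinary situation uncovered: a 30% or greater fall with a new lesion.

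The consequence is a risk of misclassification and of sites scoring differently. A loss of responders has not been shown, and its size cannot be estimated from the documents. The fall in power from 0.80 to 0.76, 0.72 or 0.63 illustrates assumed losses of 5%, 10% and 20%, and rests on the derived cut-off of 4 or more responses in 27. The design of 13/27/30 is sound on its stated inputs. The correction is worth making because it is cheap and concerns the primary endpoint.

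**What to change.** In both Section 6.3.1 (item 4) and Section 7.1:

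1. In the PR bullet, base the 30% decrease on the sum of LD of all target lesions, relative to the baseline sum LD.
2. In the same bullet, replace progression of any lesion with unequivocal progression of non-target lesions, so that growth of one target lesion counts only through the sum.
3. Add new lesions and unequivocal progression of non-target lesions to the PD bullet.
4. State that RECIST 1.1 governs where the written bullets conflict with it.

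All four changes are needed: correcting PR alone would leave a patient with a 30% fall and a new lesion uncategorised. The sample size does not change.

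The cost is the wording, plus some re-reading of scans. Stored target measurements are enough to recompute the sums. They cannot show non-target progression, for which only presence or absence had to be recorded, so existing images must be re-read for non-target status where responses were scored under the present wording. Because the trial is open-label and single-arm, and the changes to PR can only add responders relative to a literal reading, apply the same rule to every patient, not only to those near the PR boundary.

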### 7.2 Secondary endpoints

#### 7.2.1 24-weeks PFS rate

The definition of 24-week PFS rate is the percentage of patients who had **NOT** has an event before or at 24-week after treatment starts. An event is defined as follows:

- Disease progression (PD according to RECIST 1.1)
- Death due to any cause

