#### **7.2.5 Choi criteria for objective response rate assessment**

Choi criteria are based on changes in tumor size and density following contrast administration on the CT scan. By Choi, radiological PR is defined by the presence of a decrease in tumor size  $\geq 10\%$  or a decrease in tumor density/contrast enhancement (CE) on CT scan/MRI  $\geq 15\%$ ; progression (PD) is defined by the appearance of new lesions or by the increase in tumor, greatest maximal diameter  $\geq 10\%$ , without any criteria for PR by tumor density/CE or by increase in tumor density/CE  $\geq 15\%$  [11].

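### Section 7.1 takes the last assessment before progression as best response, so a confirmed PR that drifts to SD is lost from the ORR; the target-only PD bullet is a lesser gap

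*Combined protocol and SAP*

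**What the plan says.** Section 7.1 contains two statements on best response. The first is "The best response as defined by RECIST 1.1 will be used for ORR assessment". The next is "The best response is defined as the most proximal response assessment before disease progression". Section 7.1 also describes a repeat image four weeks after a PR or CR and defines a confirmed response. Its ORR bullet, however, counts a CR or PR without saying that confirmation is required.

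Section 6.3.1, item 4 (headed "Evaluations included following the RECIST 1.1") and section 7.1 give the same response bullets:

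- PD is "Progressive disease (PD): A 20% or greater increase in the sum of LD of all target lesions", measured from the smallest sum. New lesions and non-target lesions are not mentioned.
- PR carries a further condition: "In addition, there may be no appearance of new lesions or progression of any lesion".
- SD is the remainder: "Stable disease (SD): Neither sufficient increase to qualify for PD nor sufficient shrinkage to qualify for PR".

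Elsewhere the documents look beyond the target sum. For the Choi endpoint, section 7.2.5 says "progression (PD) is defined by the appearance of new lesions". Sections 7.2.1 and 7.2.3 define the PFS event by reference to RECIST 1.1, and 7.2.3 includes progression inside or outside the CNS.

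**The concern.** The ORR is the primary endpoint of phase II and drives both stages of the Simon design. Best response would ordinarily mean the best category reached before progression. The sentence in 7.1 selects the last one instead. A patient who responds, has the response confirmed, regrows into the SD range and then progresses is scored as SD. With about five responders expected, each one matters.

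The lesser concern is that the PD bullet gives no category for some scans. Two readers could then classify the same scan differently, one from the bullet and one from the named criteria, and date progression differently for PFS.

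**Working it through.** **1. The plan's own design.** Inputs from section 8.1: P0 = 5%, P1 = 20%, type I error 0.05, power 80%, stop if there are 0 responses in 13, 27 evaluable patients in total. The final cut-off is not stated. The probability of success with a cut-off of k responses is

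P(p) = Σ (x = 1 to 13) Bin(13, x, p) × Pr[Bin(14, p) ≥ k − x].

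| k | alpha at 5% | power at 20% |
|---|---|---|
| 3 | 0.135 | 0.898 |
| 4 | 0.042 | 0.801 |
| 5 | 0.010 | 0.645 |

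Only k = 4 meets both targets, so the design reproduces with a derived cut-off of 4 or more of 27. Enrolment also reproduces: 27/0.9 = 30.

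**2. The best-response sentence on one patient.** Scans follow the schedule in 6.3.2, with the confirmation image four weeks after week 8. The lesion sums are invented for illustration. No new lesion appears.

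| Time | Target sum | Change from baseline | Change from smallest sum | Category |
|---|---|---|---|---|
| Baseline | 100 | – | – | – |
| Week 8 | 65 | −35% | – | PR |
| Week 12 | 65 | −35% | 0% | PR, confirmed |
| Week 16 | 72 | −28% | 72/65 = +10.8% | SD |
| Week 24 | 80 | −20% | 80/65 = +23.1% | PD |

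The last assessment before PD is week 16, so the sentence gives SD. The best category before PD is PR. No new lesion is involved, so the reading of the PD bullet makes no difference.

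Direction: if the last assessment before PD is a response, the best one is too. The reverse does not hold. With the confirmation rule held fixed, the sentence can only remove responders.

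**3. Illustrated effect on power.** Let s be the share of true responders lost. The documents give no value for s, so it is an assumption. Counted ORR = 0.20 × (1 − s), entered in the formula above with k = 4.

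| s | Counted ORR | Expected responders of 27 | Power |
|---|---|---|---|
| 0% | 20% | 5.40 | 80.1% |
| 5% | 19% | 5.13 | 76.5% |
| 10% | 18% | 4.86 | 72.4% |
| 20% | 16% | 4.32 | 62.9% |

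One lost response reverses the final result only when the true count is exactly 4 of 27. At a true ORR of 20%, the probability of passing stage 1 with exactly 4 of 27 is 15.6%.

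**4. The PD bullet taken literally, with a new lesion present.**

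- Targets down by 30% or more: not PR (new lesion), not PD (no 20% growth), not SD (shrinkage is sufficient). No category applies.
- Targets short of a 30% fall from baseline and less than 20% above the smallest sum: SD by default.

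If a new lesion is added at week 16 in the table above, the literal bullets still give SD at week 16 and PD at week 24. If the new lesion counts as progression, PD falls at week 16 and the assessment before it is the confirmed PR.

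**5. Illustrated effect on 24-week PFS under the literal bullet.** Suppose a share q of first progressions is called one scheduled scan late. Only those first seen at week 24 change status, so the shift is q × [S(16) − S(24)]. Both q and exponential PFS with a median of 3 to 6 months are assumptions.

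- Median 3 months: S(24) = 0.279, difference 0.148.
- Median 6 months: S(24) = 0.529, difference 0.125.
- Shift: 1.3–1.5 points at q = 10%, 2.5–3.0 at 20%, 3.8–4.4 at 30%.

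That is 0.3 to 1.2 of 27 patients. For scale, 12/27 has an exact 95% interval of 25.5% to 64.7%.

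**The case against.** RECIST 1.1 is named throughout: in the heading of the bullets, in 7.1 for response and best response, and in 7.2.1 and 7.2.3 for progression. The PR bullet itself speaks of new lesions and of any lesion progressing, so the authors' idea of progression is plainly wider than the target sum. On this view the bullets are a summary and the named standard fills the gap. For the PD bullet this largely stands. What remains is a missing sentence on precedence.

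A reader might infer that the trial does not count new lesions as progression, or that its PFS will be materially inflated. The documents do not support either. The PFS event is defined by reference to RECIST 1.1, and the effect is small even on the literal reading. Losing a PR through a new lesion would also need the investigator to see it, not call progression, and scan again. Treatment ends at progression (5.5), and after end of treatment only survival follow-up is listed (6.3.4; 6.5, footnote i).

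The same defence is weaker for best response. Section 7.1 names RECIST 1.1 and then gives its own explicit rule, so naming the standard does not remove that rule. The drift from PR to SD happens on treatment and needs no unusual conduct.

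It is also fair to object that s is invented and, as a total share lost, does not separate the two mechanisms. A reader might infer that the trial really has 62.9% power. That is not supported: the figure is conditional on an assumed 20% loss.

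**Conclusion.** The best-response sentence is wrong as written and should be changed. Followed literally, it turns a confirmed PR into a non-response whenever the patient passes through SD before PD, which biases the primary endpoint downward. The direction is certain with the confirmation rule held fixed. The size is unknown, and the power figures show sensitivity only. They rest on the assumed s, a true ORR of 20% and the derived cut-off of 4 of 27. The sample size itself is not in error.

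The PD bullet is a minor drafting gap. It matters only if someone applies it in place of the named criteria. None of the power loss can be assigned to it specifically.

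**What to change.** 1. In 7.1, replace the best-response sentence with: *Best response is the best response recorded from start of treatment until first disease progression.*
2. In the ORR bullet, state whether the confirmation described in 7.1 is required. This is a separate ambiguity and should be settled openly. If unconfirmed responses would otherwise count, requiring confirmation could lower the ORR, so the net direction of changes 1 and 2 together is not assured.
3. In 6.3.1 and 7.1, add one sentence: for endpoint classification, RECIST 1.1 in full governs over the summary bullets. Derive one overall response per scan and use it for ORR, best response, PFS and 24-week PFS.
4. Section 5.5 also uses the term disease progression. That passage and the endpoint definition must be reconciled; no treatment-stopping rule is proposed here.

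The cost is a few sentences, plus a check of new-lesion and non-target status on some scans already read. The study is open-label and its protocol is at version 5.0, so the change should be dated before the final response tally. The ORR should also be reported under the old wording, so that the effect of the change is visible.

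### Progression is written as a 20% rise over the smallest sum with no minimum absolute increase, so in very small target sums a reading difference of 2 to 4 mm meets the written rule

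*Combined protocol and SAP*

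**What the plan says.** Progression is spelled out twice in the same words, in section 6.3.1 item 4 and in section 7.1: "Progressive disease (PD): A 20% or greater increase in the sum of LD of all target lesions". In both places the comparison is with the lowest sum seen so far, baseline included. No absolute increase is attached in either place or elsewhere.

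Small target sums are admissible. Section 3.1 item 3 asks for one measurable tumor. Section 6.3.1 lets a solitary lesion serve as the target and sets the lower limit at 10 mm on spiral CT (20 mm with conventional techniques). On technique, item 2 says: "Spiral CT should be performed using a 5 mm contiguous reconstruction algorithm".

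The consequences are also written down:
- Section 5.5: "Patients may continue on study therapy until disease progression or until unacceptable toxicity occurs". Progression is then listed among the events that take a patient off therapy.
- Section 7.2.1 counts as an event "Disease progression (PD according to RECIST 1.1", and section 7.2.3 does the same for PFS.
- Section 7.1: progression at the first evaluation fixes best response as PD.
- Section 6.3.2: the investigator scores response locally. Responses get a confirmatory scan; progression does not.

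Sections 6.3.1, 7.1, 7.2.1 and 7.2.3 all name RECIST 1.1 as the standard, without reproducing it.

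**The concern.** A purely relative threshold shrinks with the lesion, while reading error in millimetres need not. The reference is the smallest sum so far, so each low reading lowers the bar for the next scan and the chance of crossing it by error alone builds up over scans. The rule also reaches patients who started with larger sums and shrank into the small range.

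Two records scored literally show this. A single lesion read at 12, 11 and 13.2 mm has progressed on a change of 2.2 mm. A responder read at 12, 8, 8 and 9.6 mm has progressed on 1.6 mm.

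A false progression is a PFS event and ends study therapy. The plan also leaves two possible readings, the written bullet or the full criteria it names. Two institutions score locally (section 10.6), so the same scan could be called differently.

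**Working it through.** **Plan's own figure.** The only number the plan attaches to progression is the 20%. Its sample size (section 8.1) reproduces: a minimax search with 5% versus 20% gives 0/13 then 3/27, with type I error 0.042 and power 0.801, and 27/(1 − 0.10) = 30. Nothing below changes it.

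**Threshold in millimetres.** Threshold = 0.20 × smallest sum: 2 mm at 10, 2.4 mm at 12, 3 mm at 15, 4 mm at 20, 5 mm at 25 and 10 mm at 50.

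**One scan, no true change.** Let both readings be normal around true size L, where s is the SD of the reading of the target sum. The chance that week 8 is at least 1.2 times baseline is Φ(−0.2L / (s√(1 + 1.2²))) = Φ(−0.2L / 1.562s). With s = 1.0 mm:
- L = 10: Φ(−1.28) = 10%
- L = 12: Φ(−1.54) = 6%
- L = 20: Φ(−2.56) = 0.5%

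**By week 24.** Simulation of 400,000 patients per setting, with readings at baseline and weeks 8, 16 and 24, each judged against the running minimum. The 5 mm minimum in the last column is only an illustration; the value is not in the documents.

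| Constant sum | s = 0.5 | s = 1.0 | s = 1.5 | s = 1.0 with 5 mm minimum |
|---|---|---|---|---|
| 10 mm | 2.7% | 37% | 61% | 0.1% |
| 12 mm | 0.6% | 25% | 51% | 0.1% |
| 15 mm | 0.04% | 13% | 37% | 0.1% |
| 20 mm | 0% | 3% | 19% | 0.1% |
| 50 mm | 0% | 0% | 0.01% | 0% |

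At s = 1.5 mm the illustrative minimum leaves about 5% for the 10 to 20 mm sums. A 5 mm minimum would bind only when the smallest sum is below 5/0.20 = 25 mm.

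**24-week PFS rate.** Assume 10 to 20% of the 27 patients have sums near 12 mm (not in the documents). At s = 1.0 mm the expected false progressions are 27 × 0.10 × 0.25 = 0.7 to 27 × 0.20 × 0.25 = 1.4, or 2.5 to 5 percentage points gross. That is a loss only for patients who would otherwise be event-free at week 24. If 30 to 50% would be (assumed), the net loss is 2.5 × 0.30 = 0.75 to 5 × 0.50 = 2.5 points. Over s = 0.5 to 1.5 mm the net range is 0.10 × 0.6% × 0.30 = 0.02 to 0.20 × 51% × 0.50 = 5.1 points.

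**ORR.** False progressions at week 8 number 27 × 0.10 × 0.06 = 0.16 to 27 × 0.20 × 0.06 = 0.32. At the 20% design response rate that is 0.03 to 0.06 lost responders. This is too high for true responders: a 12 mm lesion that has shrunk 10% by week 8 has Φ((10.8 − 14.4)/1.562) = 1% false progression, and one that has shrunk 20% has about 0.1%. Even if every false progression by week 24 came before a response that would have followed, the loss is 0.7 × 0.20 = 0.14 to 1.4 × 0.20 = 0.28 responders.

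**The case against.** The strongest reply is that RECIST 1.1 governs by name, so any minimum it contains already applies and the bullets are only an abbreviated paraphrase. This is fair for the PFS endpoints, whose event is defined by reference to the criteria. It does not settle the matter. The protocol chose to print its own progression line twice, and a site following that line would score 2 to 4 mm as progression. The documents cannot show what the criteria say, so what stands is an incomplete rule open to two readings.

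The second reply is that no measurement error is documented. That is correct, and at an SD of 0.5 mm the problem nearly disappears. The 5 mm reconstruction is not evidence of error either: slice thickness is not the error of an in-plane longest diameter. A reader should not infer that noise of 2 to 4 mm has been established.

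The third is that the primary endpoint looks exposed, because first-scan progression fixes best response. A reader might infer a biased ORR or a threatened Simon decision. The arithmetic does not support that. The responder at 12, 8, 8 and 9.6 mm has a confirmed partial response before progression and still counts under section 7.1.

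Last, a prescribed millimetre value would become part of the rule that ends treatment. This objection stands, and no value is proposed here.

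**Conclusion.** The point holds as a gap in the written rule, and it is worth correcting. For a constant lesion of 10 to 12 mm the false-progression risk by week 24 is roughly a quarter to a third or more at a reading SD of 1.0 mm. It is a few percent or less at 0.5 mm, and it is small at 20 mm unless the SD is well above 1.0 mm.

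The effect is confined to patients whose smallest sum is under about 25 mm (a limit that rests on the illustrative 5 mm), and their share is unknown. It falls on PFS, the 24-week PFS rate and time on treatment. Reading the gross 2.5 to 5 points as the loss in the 24-week PFS rate would overstate it, because some of these patients would have had an event anyway. These are secondary endpoints reported descriptively (section 8.2.1).

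The conclusion rests on three assumptions: independent normal reading error, the SD range, and the share of small sums. That the rule as printed has no minimum rests on none of them.

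**What to change.** Reconcile the progression bullets in section 6.3.1 item 4 and section 7.1 with the RECIST 1.1 criteria that the protocol names, so that the 20% rule carries whatever minimum absolute increase those criteria set. The sponsor should take the value from that source; if it sets none, the protocol should say so. State that this one rule governs ORR, PFS, the 24-week PFS rate and the progression named in section 5.5.

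The change is one clause in two places plus a sentence on scope, with no extra scans and no change to the 27 evaluable or 30 enrolled.

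The cost is that true growth in very small lesions may be called progression one or more scans later. For example, a 10 mm minimum growing 20% per scan (12, 14.4, 17.3 mm) is progression at the first scan as written, but only at the third under the illustrative 5 mm. Scans are 12 weeks apart after week 24, so the protocol should acknowledge this delay.
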